8. STUDY DESIGN

This is an open, single-centre, prospective, single-arm pilot study evaluating the effect of EndoBarrier[™] implantation on insulin sensitivity and beta-cell function in obese patients with type 2 diabetes. 12 subjects will be included in this pilot trial. The investigations will be performed at Medical University of Graz, Department of Internal Medicine, Division of Endocrinology and Metabolism and Division of Gastroenterology and Hepatology.

At baseline all subjects will undergo Dual-energy X-ray absorptiometry (DEXA) measurement, Botnia clamp, blood sampling as well as a meal tolerance test (MTT) and a Lactulose/Mannitol test to determine gut permeability. 4 Weeks, 36 weeks as well as 62 weeks after EndoBarrier[™] implantation all subjects will undergo the above-named tests and investigations, again. Additionally at the baseline visit as well as after one year, tissue samples and intestinal content will be collected endoscopically. This pilot trial limited in size and scope will give us insight into the actions, efficacy and safety of the EndoBarrier[™]. The results of this pilot trial will help us in calculating the sample size for a further planned trial comparing the EndoBarrier[™] against other established weight loss interventions.

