Additionally, at Visit 3 subjects will be instructed by a qualified person to consume a liquid diet the first week after EndoBarrier[™] placement, puree diet during the second week, and normal diet (1200 – 1500 kcal/day) combined with exercise and behaviour modification for the remainder of the implant duration. Participants will also be instructed to take a proton pump inhibitor (40mg BID omeprazole) starting 3 days before the implant through 2 weeks after explant. Daily multivitamin and iron supplements will be provided and recommended for use during the 52 weeks of the implant duration.

- Meal tolerance test
- Blood sampling
- Stool sampling
- Lactulose/Mannitol Test

Visit 4 (Implantation of EndoBarrier[™])

Patient preparation

- 1. Patients must be fasting for 8 hours prior to the procedure.
- 2. Patients must be started on a Proton Pump Inhibitor (40mg twice a day) three days before the procedure and continue regimen until two weeks after the device is removed.
- **3.** Spasmolytics may be used.

Sedation

4. The procedure will be performed under conscious sedation.

Procedural Step

5. Insertion will be performed according to manufacturer instructions

Visit 5 (week 4 ± 2 week)

Study visit 5 will take place not later than six weeks after the implantation of the EndoBarrier[™].

- Physical examination
- Vital signs: resting pulse and blood pressure
- Body weight
- Concomitant medication review
- Botnia clamp
- DEXA
- Adverse events assessment

• Pregnancy Test

Visit 6 (up to 3 days after V5)

Study visit 6 will take place not later than 3 days after V5.

- Meal tolerance test
- Stool sampling
- Blood sampling
- Lactulose/Mannitol Test

Visit 7 (36 weeks ± 3 weeks)

Study visit 5 will take place not later than 39 weeks after the implantation of the EndoBarrier[™]. At this

visit the sleeve will be removed.

- Vital signs: resting pulse and blood pressure
- Body weight
- Concomitant medication review
- DEXA
- Adverse events assessment
- Biospies
- Botnia clamp

Visit 8 (up to 1 week after V7)

Study visit 8 will take place not later than 1 week after V7.

- Vital signs: resting pulse and blood pressure
- Body weight
- Concomitant medication review
- Adverse events assessment
- Meal tolerance test
- Stool sampling
- Blood sampling
- Lactulose/Mannitol Test

Visit 9 (62 weeks ± 3 weeks)

Study visit 9 will take place not later than 29 weeks after the removal of the EndoBarrier[™].

• Physical examination

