14.2 Statistical analysis

All data will be checked for distribution normality. Changes in beta cell function and other variables after EndoBarrier[™] implantation will be assessed by analysis of variance (ANOVA) with repeated measures.

Additionally, the results of this pilot will be compared to already available results from a trial with comparable patients after bariatric surgery.

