- Previous GI surgery that could affect the ability to place the device or the function of the implant
- GLP-1 receptor agonist therapy

- Known ischaemic heart disease or heart failure
- History of stroke
- Active Helicobacter pylori (Note: Subjects may be enrolled if they had a prior history of Helicobacter Pylori and were successfully treated)
- Actual iron deficiency anemia
- Subjects or Family history of a known diagnosis or pre-existing symptoms of systemic lupus erythematosus, scleroderma, or other autoimmune connective tissue disorder
- Known malignancy or any other multimorbid patient condition or circumstance, which, in the opinion of the investigator, would affect the patient's ability to participate in the protocol or would put the participant at an unjustified risk

Clinical endpoints

Primary endpoints

- Change in the glucose infusion rate (Botnia Clamp) adjusted for body weight at baseline from baseline to 4 and 36 weeks after the Endobarrier implantation, respectively
- Change in early insulin response from baseline to 4 and 36 weeks after the Endobarrier implantation, respectively

Secondary endpoints

- Change in the glucose infusion rate (Botnia Clamp) adjusted for body weight at baseline from baseline to 24 weeks after the Endobarrier explantation
- Change in early insulin response from baseline to 24 weeks after the Endobarrier explantation, respectively
- Change in body mass index from baseline to 4 and 36 weeks after the Endobarrier implantation and 24 weeks after the Endobarrier explantation
- Change in body weight from baseline to 4 and 36 weeks after the Endobarrier implantation and 24 weeks after the Endobarrier explantation
- Change in HbA1c from baseline to 4 and 36 weeks after the Endobarrier implantation and 24 weeks after the Endobarrier explantation
- Change in lactulose/mannitol ratio from baseline to 4 and 36 weeks after the Endobarrier implantation and 24 weeks after the Endobarrier explantation
- Change in glucose AUC (MMT) from baseline to 4 and 36 weeks after the Endobarrier implantation and 24 weeks after the Endobarrier explantation
- Change in c-peptide AUC (MMT) from baseline to 4 and 36 weeks after the Endobarrier implantation and 24 weeks after the Endobarrier explantation
- Change in UKPDS CHD risk from baseline to 4 and 36 weeks after the Endobarrier implantation and 24 weeks after the Endobarrier explantation

Sample Size

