This study is planned as a mechanistic pilot trial to gather first data about the parameter outlined in the primary and secondary parameter section. Currently, insufficient data are available on parameters for estimating the sample size required for this pilot trial. However, previous pilot trials investigating measurements of glucose metabolism with EndoBarrier[™] have used 10-16 subjects to demonstrate improvements[25, 26]. Therefore, we aim to include 10 subjects in our trial.

Statistical Analyses

Time of statistical analysis

All statistical analyses will be performed after the completion of trial and dataset closing.

Analysis population

All analyses will be performed on the 'Intention to treat (ITT)' or 'full analysis set' population. All patients who will be randomized to treatment sequences will be considered for the ITT analysis.

Data inspection

Data will be received in Microsoft Excel format and will be imported into statistical softwares for the analysis. First, data will be inspected for data entry errors on 10% of randomly selected data. Afterwards, data will be inspected for outliers and implausible values and these data points will be verified from the clinical report forms.

Summarization of data

Qualitative variables will be summarized as frequency with corresponding percentage (%), while quantitative variables will be summarized as either mean ± standard deviation (SD) or median and interquartile range (IQR) as appropriate. Both quantitative and qualitative variables will be presented in the table.

Statistical procedures

Normality of quantitative variables will be assessed using Shapiro-Wilk tests. The choice of statistical procedures for both primary and secondary quantitative endpoints will depend upon the distribution of variables. If normality assumption is violated, no data transformation will be carried out.

The early insulin response will be estimated from the MMT using the formula (30 minutes insulin – basal insulin)/(30 minutes glucose). The AUCs are determined by the trapezoidal method. Based on IVGTT measurements, the incremental trapezoidal area of insulin and C-

peptide during the first 10 minutes after glucose administration will represent the firstphase insulin response or acute insulin response (AIR). AIR will be also measured as the sum of insulin and C-peptide concentrations during the first 10 minutes after the glucose challenge.

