Insulin sensitivity will be assessed as the mean/median glucose uptake, calculated from the glucose infusion rates during the last 60 minutes of the euglycemic clamp (GIR), which will be adjusted for baseline body weight. Changes in body weight will be analyzed as the difference in absolute total body weight, change in BMI, excess weight loss, and total body weight loss. Changes in T2DM will be analyzed as the absolute change in HbA1c, fasting plasma glucose, and changes in T2DM medication. Differences in lipid levels and blood pressure will be analyzed as absolute differences.

The repeated measures analysis of variance (ANOVA) or Friedman test will be applied to compare parameters over time and the Durbin–Conover test with Bonferroni corrections will be applied for post hoc multiple pairwise comparisons of parameters.

The weight adjusted glucose infusion rate (GIR) changes will be assessed with a multilevel non-linear mixed model with post hoc multiple comparison and Bonferroni corrections. All statistical analyses will be conducted in Stata version 17.0 and R version 4.0.

Missing data

Missing data will be treated as such, and no data will be imputed.

Level of significance

The two-sided alpha level of <0.05 will considered to decide statistical significance.

Data presentation

Baseline characteristics will be tabulated for all patients. The results of primary and secondary outcomes will be presented both in tables and bar graphs, as appropriate.

References

1. Coutinho W L, T. World Obesity Day Press Release. World Obesity Federation 2015.

4. Intensive blood-glucose control with sulphonylureas or insulin compared with conventional treatment and risk of complications in patients with type 2 diabetes (UKPDS 33). UK Prospective Diabetes Study (UKPDS) Group. *Lancet* 1998; **352**:837-853.

5. Tight blood pressure control and risk of macrovascular and microvascular complications in type 2 diabetes: UKPDS 38. UK Prospective Diabetes Study Group. *Bmj* 1998; **317**:703-713.

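### The primary GIR change is assigned to a *non-linear* mixed model with no curve, time variable or visits named; a model with visit as a factor would answer the endpoint without that ambiguity

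*SAP*

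**What the plan says.** The first primary endpoint in the SAP is "Change in the glucose infusion rate (Botnia Clamp) adjusted for body weight at baseline from baseline to 4 and 36 weeks after the Endobarrier implantation," with the two time points taken separately. The post-removal value is a separate, secondary endpoint: "Change in the glucose infusion rate (Botnia Clamp) adjusted for body weight at baseline from baseline to 24 weeks after the Endobarrier explantation". Under Statistical procedures, GIR is summarised over the last 60 minutes of the clamp and adjusted for baseline body weight.

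Three statements bear on how the change is tested:

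- SAP, Statistical procedures, opening paragraph: "The choice of statistical procedures for both primary and secondary quantitative endpoints will depend upon the distribution of variables".
- SAP, same section, later: "The repeated measures analysis of variance (ANOVA) or Friedman test will be applied to compare parameters over time", with Durbin–Conover post hoc tests. The next paragraph says that weight-adjusted GIR "changes will be assessed with a multilevel non-linear mixed model with post hoc multiple comparison and Bonferroni corrections".
- Protocol 14.2: changes after the device "implantation will be assessed by analysis of variance (ANOVA) with repeated measures".

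On design, Protocol section 8 places the follow-up tests at "4 Weeks, 36 weeks as well as 62 weeks after EndoBarrier" implantation, so there are four clamps including baseline. Protocol 10.2, Visit 7 (week 36), states that at this "visit the sleeve will be removed".

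**The concern.** A non-linear mixed model is defined by its function, and none is given. The SAP also leaves open whether time is study weeks, visit number or minutes within the clamp, which clamps enter, which effects are random, how a visit contrast is taken from the fit, and what happens on poor fit or non-convergence. A statistician could not run this primary analysis from the text.

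The design makes the gap matter. A single smooth curve over weeks would have to pass through device removal, where the trend may reverse. If the week-62 clamp is in the fit, an off-device value can then influence the on-device estimates at weeks 4 and 36. The choice of curve would be made after the data are seen. Protocol section 8 says that the pilot's results will help size a further trial, so an estimate that depends on the curve would carry forward.

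**Working it through.** There is no stated figure to reproduce: the documents give no GIR effect, SD or curve, and the sample size is not calculated. The check asks how far the week-36 estimate can move with the curve.

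**Inputs from the documents.** Clamps at weeks 0, 4, 36 and 62; removal at week 36; 10 subjects (SAP, Sample Size), hence about 10 × 4 = 40 values if each clamp gives one. The protocol says 12 subjects, which gives 48.

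**Assumptions.** The true week-36 change is set to 1. The week-4 change is a share *w* of it (0.25 to 1). The share kept at week 62 is *r* (0 to 1). Data are complete with a random intercept only, so the fixed part of the model is the least-squares fit to the four visit means (0, *w*, 1, *r*).

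**Curves**, each with an intercept *c*:
- plateau: c + a(1 − exp(−kt))
- Emax: c + a·t/(t + h)
- rise-and-fall: c + b·t·exp(−kt)

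**Result.** Week-36 estimate as a multiple of the true change, all four clamps fitted (plateau / Emax / rise-and-fall):

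| *w* | *r* = 0 | 0.2 | 0.5 | 0.8 | 1 |
|---|---|---|---|---|---|
| 0.25 | 0.50 / 0.47 / 1.00 | 0.60 / 0.57 / 1.00 | 0.76 / 0.72 / 1.00 | 0.90 / 0.87 / 1.00 | 0.98 / 0.95 / 1.00 |
| 0.50 | 0.50 / 0.50 / 1.01 | 0.60 / 0.59 / 1.00 | 0.75 / 0.73 / 1.00 | 0.90 / 0.88 / 0.99 | 1.00 / 0.97 / 0.97 |
| 0.75 | 0.58 / 0.58 / 1.03 | 0.65 / 0.65 / 1.01 | 0.75 / 0.75 / 1.00 | 0.90 / 0.89 / 1.00 | 1.00 / 0.99 / 0.98 |
| 1.00 | 0.67 / 0.67 / 1.04 | 0.73 / 0.73 / 1.01 | 0.83 / 0.83 / 0.98 | 0.93 / 0.93 / 0.99 | 1.00 / 1.00 / 1.00 |

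Most plateau entries can be checked by hand. Unless the early rise is slow (the *w* = 0.25 row), the curve meets the week-4 mean and averages the last two visits, (1 + *r*)/2: with *r* = 0.2, 1.2/2 = 0.60. If week 4 lies above that average, the fit becomes a step at the mean of the three follow-up visits: with *w* = 1 and *r* = 0, (1 + 1 + 0)/3 = 0.67.

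In percentages:
- True +10, +30, +5 at weeks 4, 36, 62: the plateau curve gives (30 + 5)/2 = +17.5 at week 36, which is 17.5/30 = 0.58 of the truth.
- True +20, +30, +24: it gives (30 + 24)/2 = +27, or 0.90.
- True +20, +30, +30: it gives +30.

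**Week 4**, also a primary time point, moves too. With *w* = 0.5 and the effect fully sustained, the rise-and-fall curve puts week 4 at 0.25, half the truth. With *w* = 0.25 and full loss, it puts week 4 at 0.59, more than twice the truth.

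**Comparators.** With visit as a four-level factor and complete data, the estimates are the visit-mean changes, so the multiple is 1.00 in every cell. A plateau curve fitted to weeks 0, 4 and 36 only also returns those means.

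**The case against.** Several points on the other side stand.

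- The SAP never says that a curve over study weeks will be fitted. Post hoc comparisons with Bonferroni correction suggest visit-by-visit contrasts, so *non-linear* may be loose wording for a model with visit as a factor. In that case there is no bias.
- A reader might infer that week-62 data certainly enter the primary estimate. The documents do not support that: the post-removal change is a separate secondary endpoint, and the SAP does not list the visits in the fit.
- *Multilevel* could mean infusion rates nested within visits within patients. Such a model can yield a level per visit and hence contrasts between visits. The SAP does not describe one, but it cannot be dismissed as failing to answer the endpoint.
- A reader might also infer two rival primary analyses for GIR. The sentence specific to GIR can fairly be read as overriding the general ANOVA/Friedman rule. What is missing is a statement that it does.
- Where a monotone curve loses most, it misfits visibly, and a non-linear curve that can turn down recovers week 36 well. However, the SAP has no fit check or fallback, and the same curve can miss week 4.
- A quadratic in time also shifts the estimates, but it is linear in its parameters and so not strictly a non-linear model. It is left out of the table.
- The replacement is not assumption-free. A random intercept imposes equal correlation between visits that lie weeks to more than a year apart, across device removal.

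These points narrow the size of the concern. They do not supply the missing model.

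**Conclusion.** The gap in the text is certain: a primary endpoint is assigned to a non-linear model that is not written down, and its precedence over the other stated methods is left unsaid. The endpoint needs no curve over weeks.

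The numerical consequence is conditional. It arises only if a curve over study weeks is fitted to all four clamps. On the assumed means, the week-36 estimate then lies between about 0.47 and 1.04 times the true change. Results of 0.47 to 0.60 need a monotone curve, 0 to 20% of the effect kept at week 62, and a week-4 effect clearly short of the week-36 effect (up to three quarters of it if nothing is kept, about half or less if 20% is). If half is kept, monotone curves lose 17–28%. If the effect is sustained, they lose 0–5%.

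It would be tempting to conclude that the planned analysis will roughly halve the week-36 effect. The documents do not support this: they give no GIR values and no curve, and other readings of the sentence carry no such bias. The point merits a change to the SAP.

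**What to change.** Delete *non-linear* and state one primary GIR analysis that takes precedence over the ANOVA/Friedman choice:

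- a linear mixed model of per-visit GIR, adjusted for baseline body weight, with visit as a categorical factor and a random subject intercept, fitted by REML with Kenward–Roger degrees of freedom;
- two prespecified contrasts, week 4 and week 36 against baseline, with Bonferroni correction over those two (0.05/2 = 0.025 each, two-sided);
- a sensitivity analysis by paired visit differences or by Friedman with Durbin–Conover, because equal correlation between visits and normality are hard to check at n = 10.

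If a curve or a within-clamp model is really intended, write out its equation, time variable, levels and random effects, the visits included, the handling of removal at week 36, how each visit contrast is obtained, and a fallback for non-convergence.

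The cost is a paragraph of SAP text and standard code in the software already named. With complete data, the point estimates equal those from the protocol's repeated-measures ANOVA. The small downside is reliance on the covariance and normality assumptions in a small sample, which the sensitivity analysis addresses.

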11 METHODS

11.1 Meal Tolerance Test (MTT)

The MTT will be performed after an overnight fast (apart from water). A standard gauge cannula will be placed into a subcutaneous vein for blood sampling. In order to prevent blood clotting in the cannula and to keep the cannula working it will be occasionally flushed with sterile normal saline. A pre-meal blood sample will be taken (- 5mins) and then all subjects will be asked to drink Fortimel compact (10 kcal/kg) over a period of 2-4 mins (time 0 mins). During the meal test further blood samples will be taken at 15, 30, 60, and 120 minutes. All samples will be used for determination of glucose and insulin. The blood at each time point will be placed into a fluoride oxalate tube (1ml) for plasma glucose and into a serum tube for insulin.

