In 2010, a duodenal-jejunal bypass liner (DJBL, Endobarrier[™], GI Dynamics, Lexington, Massachusetts, USA) was introduced and CE marked. The EndoBarrier[™] is a 60 cm long impermeable fluoropolymer sleeve-like device, which is placed endoscopically via oral route and anchored in the duodenum creating a duodenal-jejunal bypass for a maximum of 12 months. It allows transit of chyme from the stomach through the jejunum without any contact to the duodenal mucosa. Both bile and pancreatic exocrine secretions do not get in contact with chyme in the proximal jejunum, thus the DJBL mimics a duodenal-jejunal bypass and therefore induces weight loss.

A number of studies demonstrated the feasibility of implanting this device with subsequent weight reduction[12-16]. In T2DM subjects, significant improvements in glycaemic parameters after EndoBarrier[™] implantation were observed as well as an improvement of insulin resistance measured by Homeostatic model assessment – insulin resistance (HOMA-IR) [17, 18].

However, thorough investigation of insulin resistance and beta-cell function with the gold standard, namely an intravenous glucose tolerance test combined with a hyperinsulinaemic-euglycaemic clamp (Botnia clamp) is lacking so far. The aim of the current study is to explore short and longer-term effects (26 weeks after removal) of the EndoBarrier[™] implantation on insulin resistance and beta-cell function assessed by repeated Botnia clamps to further delineate mechanisms of this intervention.

As the ENDO trial investigating the effects of the Endobarrier[™] device compared to a sham intervention was terminated early due to a higher rate of hepatic abscesses than expected, speculations about reasons are ongoing. A leaky gut and changes in the upper gastrointestinal microbiome caused by the bypass-liner are discussed. Therefore, another aim of this study is to investigate potential changes in microbiome composition and gut permeability.

Research objectives

Primary objectives

The primary objective of this trial is to determine the changes in insulin sensitivity and betacell function after EndoBarrier[™] implantation during a follow up of a 36-week period in patients with T2DM and a BMI between 30.0 and 49.0 kg/m².

Secondary objectives

- To assess the beta cell insulin response to oral and intravenous glucose loads early (4 weeks) and 36 weeks after EndoBarrier[™] implantation as well as 26 weeks after removal of the duodeno-jejunal bypass device.

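### Early insulin response (EIR), a primary endpoint, goes to a test that can discard a subject's measured data after one missed visit; its visit set and the rule for incomplete subjects are unstated

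*SAP*

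**What the plan says.** The SAP's primary endpoints include "Change in early insulin response from baseline to 4 and 36 weeks after the Endobarrier implantation, respectively". The same variable is a secondary endpoint at 24 weeks after explantation. The primary objective covers change "during a follow up of a 36-week period in patients with T2DM".

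The other primary endpoint, the weight-adjusted glucose infusion rate, has its own mixed model. EIR falls under the general rule in Statistical procedures: "The repeated measures analysis of variance (ANOVA) or Friedman test will be applied to compare parameters over time", chosen by a Shapiro-Wilk check, with Durbin-Conover and Bonferroni-corrected pairwise comparisons afterwards.

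The whole Missing data section reads "Missing data will be treated as such, and no data will be imputed". Under Analysis population the SAP states "All analyses will be performed on the 'Intention to treat (ITT)' or 'full analysis set' population". Protocol 14.2 names repeated-measures ANOVA only and has no missing-data rule.

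**The concern.** Two things are left open for EIR: whether the test over time uses three visits (baseline, 4 and 36 weeks) or also the late visit after explantation, and how a subject with a gap is treated.

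They interact. Friedman needs a value at every visit entered, and so does repeated-measures ANOVA when it is run on complete blocks. One missed visit then removes all of that subject's EIR values from the test. On the four-visit reading, absence at the late follow-up visit, which is not part of the primary endpoint, takes measured week-4 and week-36 data out of a primary comparison. That fits poorly with an intention-to-treat analysis set.

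Missing EIR values are foreseeable:
- "The early insulin response will be estimated from the MMT using the formula" shows that EIR comes from the meal test. It needs basal insulin, 30-minute insulin and 30-minute glucose. Protocol 11.1 takes one pre-meal sample, and then "During the meal test further blood samples will be taken at 15, 30, 60, and 120 minutes".
- The meal test is on a different visit from the clamp (V3, V6, V8 and V10 in Protocol 10.1). For example, "Study visit 6 will take place not later than 3 days after V5".
- Protocol 9.4 provides for withdrawal after adverse events and for loss to follow-up.

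With 10 subjects (SAP) or 12 (Protocol), each one dropped costs visible precision. Protocol 8 also says the results will help size a further trial.

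**Working it through.** **Inputs.** N = 10 (SAP, Sample Size) or 12 (Protocol 8); two-sided alpha 0.05 (SAP, Level of significance). The documents give no effect size, SD, power or missed-visit rate, so there is no figure of the plan's own to reproduce. Assumed: baseline always observed; each follow-up visit missed independently with probability m = 5, 10 or 15%.

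**Step 1: expected complete subjects**, N(1 - m)^k, where k is the number of follow-up visits that must be present.

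| N | m | one contrast (k=1) | baseline, 4, 36 weeks (k=2) | all four visits (k=3) |
|---|---|---|---|---|
| 10 | 5% | 9.5 | 9.0 | 8.6 |
| 10 | 10% | 9.0 | 8.1 | 7.3 |
| 10 | 15% | 8.5 | 7.2 | 6.1 |
| 12 | 5% | 11.4 | 10.8 | 10.3 |
| 12 | 10% | 10.8 | 9.7 | 8.7 |
| 12 | 15% | 10.2 | 8.7 | 7.4 |

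The chance that at least one subject is incomplete on the three-visit set is 1 - (1 - m)^(2N). For N = 10 this is 64%, 88% and 96%; the expected number lost at 10% is 10 - 8.1 = 1.9.

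**Step 2: precision.** The 95% CI half-width for a paired change, in SDs of the change, is t(0.975, n-1)/√n: 0.925 for n=7, 0.836 for 8, 0.769 for 9, 0.715 for 10 and 0.672 for 11. At m = 10%, rounding n:
- Three visits against one contrast: N=10, 0.836/0.769 = 1.09; N=12, 0.715/0.672 = 1.06.
- Four visits against one contrast: N=10, 0.925/0.769 = 1.20; N=12, 0.769/0.672 = 1.14.

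Averaging over the binomial distribution of n instead of rounding, the three-visit loss at 5, 10 and 15% is +4, +9 and +16% (N=10) and +4, +8 and +14% (N=12).

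**Step 3: the Bonferroni family depends on the same choice.** Three visits give 3 pairs, 0.05/3 = 0.0167 each. Four visits give 6 pairs, 0.05/6 = 0.0083 each.

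**Step 4: bias, conditional on assumptions.** Simulation with N = 10, three visits, true changes 0.50 SD (week 4) and 0.80 SD (week 36), week 36 missing in 20%, and several covariance structures.
- Loss unrelated to response: completer means are 0.50 and about 0.80, so unbiased.
- Loss likelier after a small week-4 change (log-odds 1 per SD): completers give 0.61-0.68 and about 0.89. An unstructured likelihood fit to all observed data gives 0.50 and 0.79-0.81.

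**Step 5: accuracy in that second case** (root mean squared error, RMSE; compound symmetry, then AR(1) with correlation 0.7).
- Week 4: completers 0.38 and 0.29; all observed data 0.32 and 0.24.
- Week 36: completers 0.367 and 0.362; unstructured fit 0.392 and 0.363. Coverage of the completer 95% CI stays near 94%.

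**The case against.** The strongest reply has four parts.

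*The visits are already listed.* Mostly true. For BMI, weight, HbA1c, lactulose/mannitol ratio, the AUCs and UKPDS risk, the SAP's endpoint list gives baseline, 4, 36 and post-explant weeks. The real ambiguity is EIR, which is split between primary and secondary; the primary objective makes baseline, 4 and 36 weeks the natural set. What remains is that the SAP does not say so for the test or for its pairwise family.

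*The SAP does not prescribe deletion.* Also true. A reader might infer that the plan commits to a complete-case analysis. It does not: an ANOVA fitted with subject and time effects can keep incomplete subjects. But Friedman is one of the two named tests and cannot do so in its standard form.

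*The loss is small and assumed.* At 5-10% missed, the three-visit set costs 4-9% in interval width, and the plan states no power for this to breach. Fair; this limits the weight of the point.

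*A mixed model is not clearly better.* Partly right. At week 36 it removes the bias without lowering RMSE, and at week 4 simply using every available pair brings the gain. Making a normal-theory model primary even when normality fails would also override the SAP's choice of test by distribution. The fix therefore keeps the rank route in that case.

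**Conclusion.** The concern holds in limited form. For EIR, the SAP leaves open the visit set of the test and the handling of incomplete subjects, and one of its two named tests discards a subject's measured primary data after a single missed visit. At an assumed 10% missed per follow-up visit, the cost is an interval roughly 6-9% wider on the three-visit set, and up to about 20% wider if four visits are pooled. These figures rest on independent missingness and on a rate the documents do not give.

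A reader might infer that the primary EIR results will be biased. The documents do not support that. Bias needs loss related to response and changes reported for completers only. Friedman and Durbin-Conover yield p-values, and the SAP's descriptive summaries are not restricted to completers. If completer-only changes were nevertheless used to size the next trial, the error would carry forward.

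This should be fixed before analysis, because it concerns a primary endpoint in a very small trial and the repair is cheap.

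**What to change.** 1. Run the primary EIR test on baseline, 4 and 36 weeks only. Test the late post-explant contrast separately, and fix the Bonferroni family to match.
2. Where the SAP would use repeated-measures ANOVA, replace it with a linear mixed model on all observed data: visit as a categorical factor, REML, small-sample degrees of freedom, and no assumed compound symmetry. If that is not estimable, fall back on paired changes from all available pairs.
3. Where normality fails, keep the rank route, but base each pairwise contrast on all subjects observed at both visits. Name the paired rank test used, and report n per contrast and the number excluded from Friedman.

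Cost: SAP wording and minor programming in the Stata and R versions already named; no new data.

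Downside: the model relies on data missing at random and on a covariance estimated from few subjects. The main gain is precision at week 4; at week 36 it protects against bias without lowering RMSE. The available-pairs fallback does not remove week-36 bias if loss depends on response. If the sponsor prefers not to add a model, stating the visit set, the Bonferroni family and the rule for incomplete subjects would still close the main gap.
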